5.2.2.3 Continuous Renal Replacement Therapy Dialysate

Sites will be instructed to use only commercially available standard CRRT sterile dialysate solutions having a density similar to saline solutions (close to 1) with the Prismaflex System. Dialysate formulation and flow rate are prescribed in accordance with the patient's clinical needs and each institution's standard clinical practice for CRRT.

For the Prismocitrate 18 Arm, the dialysate should have a bicarbonate concentration that accounts for the significant buffer load provided by Prismocitrate. Study sites will also ensure that the dialysate contains no calcium in the Prismocitrate 18 Arm.

5.2.2.4 Continuous Renal Replacement Therapy Replacement Fluids/Solutions

In the Prismocitrate 18 Arm, both Prismocitrate 18 and an intravenous-quality solution infused post-dilution will serve as the replacement fluids/solutions. Prismocitrate 18 will be delivered to the extracorporeal circuit by the Prismaflex System PBP via the PBP infusion line. The use of a calcium-containing post-dilution solution is not recommended in the Prismocitrate 18 Arm.

For the Control Group, replacement fluids (including one infused post-dilution) should be prescribed according to institutional practice at the investigative site.

5.2.2.5 Anticoagulants and Dosing/Administration of Prismocitrate 18

Either Prismocitrate 18 or no systemic anticoagulant will be used in this study. Prismocitrate 18 will be infused at a minimal initial rate of 1000 mL/hour. The rate will be titrated to maintain post-filter blood iCa levels < 0.4 mmol/L.

5.2.3 Monitoring of Therapy

Systemic iCa levels will be measured at baseline, initiation, and systemic and post-filter blood iCa levels will be measure 1 hour after initiation of study CRRT (post-randomization) and then every 6 hours thereafter and at 120 hours or end of Treatment Period. The pH and bicarbonate should be measured at baseline, initiation, and every 6 hours during the 120 hour Treatment Period and at 120 hours or end of Treatment Period. Health care professionals managing the patient should be instructed to notify the clinician immediately if the serum pH is < 7.20 or > 7.45, serum bicarbonate is < 15 or > 35 mmol/L, and/or the systemic blood iCa is < 0.9 or > 1.3 mmol/L.

Citrate metabolism may be impaired in patients with moderate to severe liver failure. The additional steps outlined below are needed to monitor specifically for the potential development of citrate accumulation, not only in these patients but in the entire study

population. Blood total calcium concentrations will be measured at baseline, initiation, 1 hour and every 6 hours during the 120 hour Treatment Period and at 120 hours or end of the Treatment Period from the initiation of study CRRT. In conjunction with simultaneous systemic iCa concentrations, the total calcium/iCa ratio (both measurements in mmol/L) will be determined as an indicator of citrate accumulation and health care professionals managing the patient should be instructed to notify the clinician for any value above 2. 1. Moreover, based on the clinical judgement of the managing physician, this threshold value should also prompt an immediate CRRT prescription change designed to correct the metabolic disturbance. One of the following prescription changes should occur:

- Decrease in the Prismocitrate infusion rate; or
- Increase in the BFR; or
- Increase in the dialysate flow rate

The effect of one of these changes should be assessed with ongoing monitoring of relevant clinical and laboratory parameters - if improvement does not occur within two (2) hours, the Prismocitrate infusion should be stopped.

When a total calcium/iCa ratio of more than 2.1 is reported, any one of the following abnormalities reported concurrently should heighten the clinical suspicion of citrate accumulation and reinforce the need to undertake the steps outlined above:

- Decrease in iCa concentration to less than 1.1 mmol/L (despite adequate calcium compensation). Decrease in pH to value less than 7.20 or decrease in base excess (threshold value: -5 mmol/L).
- Increase in anion gap to more than 11 mmol/ L

Serum electrolytes (sodium, potassium, chloride, bicarbonate, phosphate, magnesium and anion gap) and base excess should be recorded at baseline, initiation, every 6 hours during the 120 hour Treatment Period and at 120 hours or end of Treatment Period. Coagulation parameters, hemoglobin, and hematocrit will be recorded at least once daily.

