3.5 Study Product and Material

Prismocitrate 18 is an investigational CRRT solution developed by the Sponsor and provided to the participating sites for use as a replacement solution containing an

anticoagulant to prevent clotting of the extracorporeal circuit. All other solutions used for standard-of-care CRRT are to be provided by the investigational site.

Prismocitrate 18 Solution contains standard electrolytes (sodium and chloride) and citrate.

Table 1 shows Composition of Prismocitrate 18.

Table 1. Prismocitrate 18

Name of the Substance	Quantity for Prismocitrate 18 (g/L)
Sodium chloride	5.03
Sodium citrate	5.29
Composition	Prismocitrate 18 (mmol/L)
Citrate	18
Sodium	140
Chloride	86

Water for injections to 1,000 mL.

Hydrochloric acid for pH adjustment.

Theoretical Osmolarity=244 mOsm/L and pH≈7.4.

Prismocitrate 18 acts as both an anticoagulant for the extracorporeal circuit and a replacement solution to compensate for water and electrolytes removed in the filter effluent and achieve solute clearance through convection. Therefore, this solution would be indicated for continuous venovenous hemodiafiltration (CVVHDF). The pre-filter infusion rate of Prismocitrate 18 (based on its citrate concentration) is indexed to the blood flow rate (BFR) to achieve a target blood citrate concentration of 3 - 5 mmol/L of blood, manifested as a post-filter blood iCa concentration of < 0.4 mmol/L. Moreover, the rate of calcium reinfusion is guided by a target systemic blood iCa of 0.9 - 1.3 mmol/L. In the protocol, specific instructions regarding prescription adaptations to achieve these targets will be provided in Section 5.2.1.

In addition to its role as a replacement solution and anticoagulant, Prismocitrate 18 also is a buffer source through the metabolism of citrate to bicarbonate by the patient. Therefore, the prescription of Prismocitrate 18 is made according to the patient's fluid removal requirements, additional fluid inputs and outputs, and the desired acid-base and electrolyte balances. Moreover, Prismocitrate 18 is prescribed relative to the flow rates of the other therapeutic fluids used during CRRT (replacement fluid and/or dialysate). A

dedicated anticoagulation pump and infusion line, incorporated into the CRRT system and extracorporeal circuit, respectively, are required for the administration of Prismocitrate 18

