5.2.2.2 Initial Prescription Orders for the Prismocitrate 18 Arm

This initial prescription only applies to patients randomized to the Prismocitrate 18 Arm.

- Blood Flow Rate (Q_B): 100 to 200 mL/minute.
- The anticoagulant/replacement solution to be used is Prismocitrate 18, which at final concentration will provide: 140 mmol/L sodium, 86 mmol/L chloride, 18 mmol/L citrate.
- Minimal Initial Flow rate (mL/hour) of Prismocitrate 18 (delivered from the Prismaflex System PBP scale by the PBP pump): 1000 mL/hour.
 - The flow rate can be titrated by 100 mL/hour increments to maintain post-filter blood iCa levels < 0.4 mmol/L.

Rinse and prime the Prismaflex M150 Set according to the IFU. No heparin containing solutions should be used for priming.

After the initial citrate protocol prescription, the general guidelines outlined in Section 5.2.2 should be followed.

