5.2.2.2.1 Effluent Rate

Total effluent rate (Q_E) (mL/hour) = Pre-blood pump (PBP) infusion rate (Q_{PBP}) + Post-dilution replacement fluid rate (Q_R) + Dialysate rate (Q_D) + patient fluid removal rate (Q_{FR}) .

- QPBP corresponds to the infusion rate of Prismocitrate 18.
- As specified in the Prismaflex M150 Set IFU, post-filter replacement fluid should be prescribed according to institutional practice for proper functioning of the deaeration chamber. The use of a calcium-containing post-dilution solution is not recommended.
- To calculate the hourly effluent rate to be prescribed, assume the effluent rate is a surrogate for the daily CRRT dose and the minimum prescribed dose is 25 mL/kg/hour with a minimum target delivered dose of 20 mL/kg/hour per 24 hours dose of treatment for both groups.
- The required effluent rate (mL/hour) can then be calculated by multiplying the patient weight (in kg) at the time of CRRT initiation by the target prescribed dose.
- For example, a 90 kg patient would require a total effluent rate of 2,250 mL/hour (90 kg x 25 mL/kg per hour). While adjustments in the infusion rates of Prismocitrate 18, post-dilution replacement solution, and dialysate can be titrated to meet the desired metabolic and anticoagulation requirements for the patient, the total effluent rate should not appreciably change, with maintenance of a minimum prescribed dose of 25 mL/kg/hour.

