5.2.2.2 Blood Flow Adjustments

Based on the anticoagulation and metabolic requirements of the patient, a change in BFR should prompt consideration of the need for concomitant changes in the citrate infusion, post-dilution replacement fluid, and dialysate rates (as described in Section 5.2.2.2.1).

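### Raising blood flow, one of three listed responses to suspected citrate accumulation, does not lower the citrate load and increases it slightly at a held Prismocitrate rate

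*Protocol*

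**What the plan says.** Protocol Section 5.2.3 (Monitoring of Therapy) sets the response to a total calcium/iCa ratio above 2.1. Subject to the managing physician's judgement, "this threshold value should also prompt an immediate CRRT prescription change designed to correct the metabolic disturbance". It continues: "One of the following prescription changes should occur". The three items are a lower Prismocitrate rate, "Increase in the BFR; or" a higher dialysate flow. The effect of the chosen change is then watched, and "if improvement does not occur within two (2) hours, the Prismocitrate infusion should be stopped".

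Three other places bear on how the Prismocitrate rate follows BFR:

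- Section 3.5 says the pre-filter rate "is indexed to the blood flow rate (BFR) to achieve a target blood citrate concentration of 3 - 5 mmol/L of blood".
- Section 5.2.2.2 (Initial Prescription Orders for the Prismocitrate 18 Arm) says: "The flow rate can be titrated by 100 mL/hour increments to maintain post-filter blood iCa levels < 0.4 mmol/L".
- The Blood Flow Adjustments section says that "a change in BFR should prompt consideration of the need for concomitant changes in the citrate infusion". It gives no direction.

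None of these ties a BFR increase made under Section 5.2.3 to a citrate reduction.

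**The concern.** The three items are alternatives, so a BFR increase alone satisfies the instruction. The step is meant for a patient who may be failing to metabolise citrate, and what matters then is the citrate per hour returned to the patient: citrate infused minus citrate lost in effluent. BFR does not enter the infused amount. It does enter the removal, because more blood past the same infusion means a lower citrate concentration at the filter and less citrate in each litre of effluent.

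One listed option therefore appears to push the opposite way from the other two. A physician could choose it in good faith and leave infused citrate unreduced for up to two hours. If the Prismocitrate rate were raised along with BFR, as the indexing in Section 3.5 and the post-filter iCa target could suggest, infused citrate would rise in proportion. Section 5.2.3 does not say that the rate must be held.

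**Working it through.** **Inputs from the documents**

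- Prismocitrate citrate: 18 mmol/L (Section 3.5, Table 1).
- BFR in the Prismocitrate arm: 100 to 200 mL/min, or 6 to 12 L/h (Section 5.2.2).
- Minimum pre-blood pump rate: 1,000 mL/h (Section 5.2.2).
- Effluent: "a 90 kg patient would require a total effluent rate of 2,250 mL/hour" (Section 5.2.2.2.1). Check: 90 × 25 = 2,250 mL/h.
- Citrate target: 3 to 5 mmol per litre of blood (Section 3.5). Check: 18 × 1.0 / 6 = 3.0 at 1,000 mL/h and 100 mL/min, the lower end of the target.

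**Assumptions not in the documents**

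Effluent equilibrated with filter blood; hematocrit 0 to 30%; systemic citrate c_s = 0 in the base case.

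**Formula** (flows in L/h)

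Net citrate = 18·Q_PBP − Q_E·(Q_B·c_s + 18·Q_PBP)/(Q_B + Q_PBP)

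Q_B is multiplied by (1 − hematocrit) when citrate is taken to be in plasma only.

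**Rate held, Q_E = 2.25, c_s = 0**

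| Step | Hematocrit | Before (mmol/h) | After (mmol/h) | Change | Extra over 2 h (mmol) |
|---|---|---|---|---|---|
| 150→200 mL/min at 1,500 mL/h | 0 | 27 − 2.25×27/10.5 = 21.21 | 27 − 2.25×27/13.5 = 22.50 | +6.1% | 2.6 |
| same | 30% | 19.21 | 20.86 | +8.6% | 3.3 |
| 100→200 mL/min at 1,000 mL/h | 0 | 18 − 2.25×18/7 = 12.21 | 18 − 2.25×18/13 = 14.88 | +21.9% | 5.3 |
| same | 30% | 18 − 2.25×18/5.2 = 10.21 | 18 − 2.25×18/9.4 = 13.69 | +34.1% | 7.0 |

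**Sensitivity of the size**

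- Effluent 1.75 to 3.0 L/h (70 to 120 kg at 25 mL/kg/h), hematocrit 0 to 30%: +4% to +13% for the first step, +15% to +61% for the second.
- c_s = 1 mmol/L: +6.3% to +9.0% and +24.5% to +39.2%.
- Smaller steps: 150→175 at 1,500 mL/h gives +3.4% to +4.8%; 100→125 at 1,000 mL/h gives +8.4% to +12.8%.

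**Sign**

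d(removal)/dQ_B = Q_E·Q_PBP·(c_s − 18)/(Q_B + Q_PBP)². This is negative for any systemic citrate below 18 mmol/L, so net load rises with BFR.

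Dropping full equilibration does not change this. Four clearance models (full saturation and counter-current exchange with KoA 2, 5 and 20 L/h), hematocrit 20 to 40% and c_s 0 to 3 mmol/L give 60 combinations at 1,000 mL/h. Net load rose at each step from 100 to 150 to 200 mL/min in all of them. In the counter-current models at hematocrit 30%, going from 100 to 200 lowers net load only above a systemic citrate of about 10.7 mmol/L. With the formula above at hematocrit 0, break-even at 200 mL/min with complete saturation needs starting saturation no higher than 10.5/13.5 = 78% at 150 mL/min, or 7/13 = 54% at 100.

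**The other two options**, from the same two starts, hematocrit 0 to 30%, c_s 0 to 1 mmol/L:

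- Prismocitrate −20%: net citrate −17% to −28%. The range covers effluent held and effluent falling with the cut.
- Dialysate +500 mL/h: −6% to −25%.

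**If the rate is raised with BFR** at 3 mmol per litre of blood, infused citrate goes from 3×9 = 27 to 3×12 = 36 mmol/h (150→200), or from 3×6 = 18 to 36 (100→200).

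**The case against.** The strongest reply accepts the direction and disputes the weight.

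- **Size.** The large percentages need BFR doubled in one step from the minimum settings. From 150 mL/min the rise is 3% to 9% in the base case, against 54 mmol infused over the same two hours at 1,500 mL/h. The absolute increment also shrinks as systemic citrate rises: 2.57 to 2.14 mmol over two hours for 150→200 at c_s = 3 mmol/L, hematocrit 0. This stands. The main failing is up to two hours on a step that does not help; the added load is modest.
- **Raised-rate case.** It requires a physician who suspects accumulation to give more citrate. Section 5.2.2.2 says only that the rate can be titrated; the firmer wording, that it will be, is in Section 5.2.2.5. The Blood Flow Adjustments section asks for thought, not action. This also stands: that case is possible but not ordered, and the conclusion does not rest on it.
- **Safeguards.** Exclusions 6 and 7 remove severe liver failure and refractory shock with worsening lactic acidosis. Sites must have citrate experience (Section 3.3). Section 5.2.3 lists concurrent warning signs, leaves the choice to judgement and imposes the two-hour stop. All of these limit harm, but none makes a BFR increase lower the load.
- **Missing figure.** Figure 1 of the protocol is not shown and may say how the rate follows BFR. The held-rate result does not depend on it.
- **Citrate per litre.** A higher BFR does lower citrate per litre of circuit blood. Accumulation turns on citrate per hour reaching the patient, which goes up.

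**Conclusion.** The concern holds. As written, Section 5.2.3 offers three interchangeable responses to suspected citrate accumulation, and one of them works against the other two. At a held Prismocitrate rate a BFR increase adds about 6% to 9% to net citrate from a 150 mL/min start, and 22% to 34% for the widest permitted step, at 2.25 L/h effluent and zero systemic citrate. The sizes depend on assumed hematocrit, systemic citrate and filter saturation; the direction did not change over the ranges tested.

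This is a safety instruction that should be corrected, not a defect that threatens the trial: the increment is modest from common settings and the two-hour stop bounds it. Endpoints, power and analysis are unaffected.

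**What to change.** Delete "Increase in the BFR; or" from Section 5.2.3. The two options left both lower the load. Deletion is the cleanest change and the one I recommend.

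If a BFR option is wanted, replace the line with: *Decrease in the BFR (not below 100 mL/minute) with a proportional decrease in the Prismocitrate infusion rate; or*. This keeps citrate per litre of blood unchanged. From 150 mL/min and 1,500 mL/h to 100 and 1,000, net citrate falls from 21.2 to 18 − 2.25×18/7 = 12.2 mmol/h (−42%) with effluent kept at 2.25 L/h, or to 18 − 1.75×18/7 = 13.5 (−36%) if effluent falls to 1.75. Most of that comes from the Prismocitrate cut: the same cut at an unchanged 150 mL/min already gives −34% or −30%. The replacement is not available to a patient already at 100 mL/min, and a lower BFR could affect circuit life, the primary endpoint.

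With either change, state that the 1,000 mL/h pre-blood pump minimum in Sections 5.2 and 5.2.2 does not apply to a reduction made for suspected citrate accumulation. The stop rule implies this, but a patient at the minimum otherwise faces a conflict with the first option. As a clerical matter, the pointer in Section 3.5 to Section 5.2.1 should read Section 5.2.2.

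Cost: one or two sentences in a protocol amendment and a training note.

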5.3 Selection and Timing of Dose for Each Patient

The timing and dose of the Prismocitrate infusion for the Prismocitrate Group will be prescribed and adjusted for each patient during the 120 hour Treatment Period per Section 5.2

5.4 Method of Assigning Patients to Treatment Groups

All enrolled subjects will be randomized to one of two treatment arms (Prismocitrate Group or Control Group) in a 1:1 manner using a site-stratified central randomization scheme.

5.5 Blinding

This is an open-label study that will not utilize blinding of the investigational drug. The study site team will be made aware of the treatment assignment at randomization. The study site team will be instructed to document the randomization assignment in source documents and follow their local procedure(s) to ensure their study patients receive their appropriate treatment.

5.6 Packaging and Labeling

For this clinical trial, investigational Prismocitrate 18 will be provided by the sponsor and will come packed in 5 L bags. All other solutions used in the management and care of patients in the trial will be provided by the local institution. Each bag will be labeled with a production lot number for product accountability.

Each Prismocitrate 18 product will be labeled according to local regulations. The US product will be labeled per Title 21 of the Code of Federal Regulations (CFR) Part 312.6 and Part 201. The Canadian product will be labeled per Part C, Division 5 of the Canadian Regulations.

All labels in the US will include the investigational statement:

"Caution: New Drug--Limited by Federal (or United States) law to investigational use."

All labels in Canada will include the investigational statement:

"CAUTION: New Drug – Limited by Federal Law to investigational use. To be used by qualified investigator only. Mise en garde: Nouveau medicament – Utilisation limitée à des fins de recherche par la loi fédérale. Doit être administer uniquement par des investigateurs qualifies."

5.7 Storage and Accountability

All investigational drug and clinical supplies will be manufactured, handled, stored, and provided to patients in accordance with Good Manufacturing Practice (GMP) and International Conference on Harmonization (ICH) Guidelines for Good Clinical Practice (GCP).

The investigators at each site will be supplied with the investigational product (IP), Prismocitrate 18, to be investigated during this clinical study. Prismocitrate 18 will be stored according to product label specifications, or other specific directions provided by the Sponsor.

Prismocitrate 18 must be stored in a locked area with restricted access. Prismocitrate 18 must only be used to treat patients enrolled in the study and randomized to the Prismocitrate Group under the sole supervision of the investigator.

The PI (or delegated person) at each site is solely responsible for keeping records of documents according to the following requirements:

- Date, quantity and lot numbers of Prismocitrate 18 units received by the investigator at the study site.
- Date, lot numbers and patient assignment of Prismocitrate 18 dispensed by the investigator.
- Lot numbers of damaged or destroyed Prismocitrate 18.

At each visit, the Study Monitor must ensure that the investigator has sufficient number of Prismocitrate 18 units at his/her disposition and that the Prismocitrate 18 is being used according to site requirements.

5.8 Investigational Product Destruction

If the IP, Prismocitrate 18, is determined to be unacceptable for initial or continued use, it shall be destroyed on site in accordance with the site's SOPs and replaced. The clinic coordinator will notify the Sponsor or its designee to arrange for delivery of replacement IP.

All IP will be reconciled and accounted for throughout the study. The study monitor will verify that all unused IP has been destroyed during the site close out visit. Additionally, at the conclusion of the study, records of all IPs delivery, inventory, dispensation, return, destruction, and disposition will be collected from the investigational site. If the investigational site procedures do not allow for IP destruction on site, the study monitor will arrange for the return of all unused IP.

6. STUDY PROCEDURES

6.1 Informed Consent

Patients or their legally-authorized representative will sign an ICF for the clinical study. As part of the consenting process, each ICF will be reviewed with the prospective study participants or their legal representatives, and an investigator will be available to answer questions regarding procedures, risks, and alternatives. The PI or his/her entitled designee will obtain a signed ICF from each patient or from the patient's legally-authorized representative or designee as defined by local law. Informed Consent Forms will be obtained before any protocol-specific procedures are performed.

The PI should allow the time necessary for the patient or the patient's legally-authorized representative to inquire about the details of the study after which the ICF must be signed and personally dated by the patient or by the patient's legally-authorized representative and by the person who conducted the informed consent discussion. The patient or a legally-authorized representative should receive a copy of the signed ICF and any other written information provided to the study patient. Only patients with the initial intention to complete the study should be considered for entry into the study.

The Sponsor will provide a template ICF which includes all GCP required elements. Preparation of the ICFs is the responsibility of the PI and must include all elements required by GCP and applicable regulatory requirements and must adhere to GCPs and to the ethical principles that have their origin in the Declaration of Helsinki. The language must be nontechnical and easily understood. All ICFs will be approved and reviewed by the Sponsor prior to IRB/REB review. The PI must furnish the Sponsor or its designee with a copy of each IRB/REB-approved ICF to be used in this study prior to the commencement of the study.

